#### 6.4 Day 0 (SB-318 Infusion)

Subjects will receive the SB-318 infusion at a hospital or acute care facility, remain there for at least 24 hours after the infusion for observation, and be discharged when all AEs and vital signs are stable.

The following assessments and procedures will be performed:

- Review and record concomitant medications.
- Physical examination.
- Vital signs (for frequency, refer to the Study Reference Manual).
- Assessment of AEs.
- ERT administration log.

- Pregnancy test (females of childbearing potential, only if >7 days from Baseline pregnancy testing).
- Prednisone or equivalent corticosteroid administration.
- Infusion of SB-318 via a peripheral vein catheter.

#### 6.5 Day 1

All subjects will remain in the hospital or acute care facility for at least 24 hours after completion of SB-318 infusion. Subjects will be discharged when all AEs and vital signs are stable.

The following assessments and procedures will be performed:

- Review and record concomitant medications.
- Physical examination.
- Vital signs (continued measurement from Day 0).
- Assessment of AEs.
- Clinical laboratory tests.
- Liver panel.
- Vector genome PCR in plasma (12 hours after end of SB-318 infusion).
- Prednisone or equivalent corticosteroid administration.

#### 6.6 Day 7 (+/- 1 day)

The following assessments and procedures will be performed:

- Review and record concomitant medications.
- Physical examination.
- Vital signs.
- Assessment of AEs.
- ERT administration log.
- 12-lead ECG.
- Liver panel.
- Vector genome PCR in plasma, saliva, urine, stool, and semen (males only).
- Prednisone or equivalent corticosteroid administration.

#### 6.7 Weeks 2, 4, 6, and 8 (+/- 2 days)

The following assessments and procedures will be performed unless otherwise stipulated:

- Review and record concomitant medications.
- Physical examination.
- Vital signs.

- Assessment of AEs.
- ERT administration log.
- Pregnancy test (females of childbearing potential only; at Weeks 4 and 8 only).
- Clinical laboratory tests.
- Liver panel (twice weekly; may be conducted remotely).
- GAG testing in urine.
- IDUA / GAG testing in blood.
- Circulating AFP level (at Weeks 4 and 8 only).
- Vector genome PCR in plasma, saliva, urine, stool, and semen (males only; at Weeks 2, 4, and 8 only).
- Immunogenicity assays (at Week 4 only).
- Prednisone or equivalent corticosteroid administration.

#### **6.8 Weeks 12, 16, 20, 24, 28, 32, 36, 40, 44, 48, and 52 (+/- 1 week)**

The following assessments and procedures will be performed unless otherwise stipulated:

- Review and record concomitant medications.
- Physical examination (at Weeks 12, 16, 20, 24, 36, and 48 only).
- Vital signs (at Weeks 12, 16, 20, 24, 36, and 48 only).
- Assessment of AEs.
- ERT administration log.
- JROM (at Weeks 24 and 48 only).
- Neurologic cranial nerve exam and muscle strength testing of the upper extremities (at Weeks 24 and 48 only).
- 12-lead ECG (at Weeks 24 and 48 only).
- ECHO (at Week 48 only).
- Pregnancy test (females of childbearing potential only; at Weeks 12, 16, 20, 24, 36, and 48 only).
- Clinical laboratory tests (at Weeks 12, 16, 20, 24, 36, and 48 only).
- Liver panel (twice weekly until Week 20; then at Weeks 24, 28, 32, 36, 40, 44, 48, and 52; may be conducted remotely until Week 20 and at Weeks 28, 32, 40, 44, and 52).
- Chimerism assay (at Weeks 12 and 48 only; for post-HSCT subjects only)
- GAG testing in urine.
- IDUA / GAG testing in blood (at Weeks 12, 16, 20, 24, 36, and 48 only).
- Circulating AFP level (at Weeks 12, 24, and 48 only).

- Vector genome PCR in plasma, saliva, urine, stool, and semen (males only) (at Weeks 12, 16, 20, 24, 36, and 48 only).
- PFTs (at Weeks 24 and 48 only).
- 6MWT (at Weeks 24 and 48 only).
- Visual acuity test and corneal clouding exam (at Weeks 24 and 48 only).
- Neurocognitive abilities tests by WASI-II, WPPSI-IV, or BSID-III, and by VABS-II (at Weeks 24 and 48 only).
- MRI of liver (at Weeks 24 and 48 only).
- MRI of brain and cervical spine (at Week 48 only).
- ACTH stimulation (cosyntropin) test (at Week 20 only or at end of prednisone or equivalent corticosteroid taper; see [Appendix 3](#)).
- Liver biopsy (at Weeks 24 and 48 only).
- Lumbar puncture (at Weeks 24 and 48 only).
- Immunogenicity assays (at Weeks 12, 24, 36, and 48 only).
- Prednisone or equivalent corticosteroid administration (through Week 20 only).

#### **6.9 Months 15, 18, 21, 24, 27, 30, 33, and 36/End of Study (+/-1 month)**

Subjects will be evaluated every 3 months in Years 2 and 3 after SB-318 infusion.

An End of Study (EOS) visit will be conducted at Month 36.

At the EOS visit, subjects will be asked to participate in the LTFU Study. Study subjects may participate in the LTFU Study after 12 months of follow-up in this study, in which case an EOS visit may be conducted anytime after Week 52 but before the next scheduled study visit. Study participants who wish to enroll in the LTFU Study with less than 12 months of follow-up in this primary study may be considered on a case-by-case basis at the judgement of the Principal Investigator and after consultation with the Sponsor. In these cases an EOS visit may be conducted anytime when transition to the LTFU study is imminent. Informed consent will be obtained prior to participating in the LTFU Study.

The following assessments and procedures will be performed unless otherwise stipulated:

- Review and record concomitant medications.
- Physical examination.
- Vital signs.
- Assessment of AEs.
- ERT administration log.
- JROM (at Months 18, 24, 30, and 36/EOS only).
- Neurologic cranial nerve exam and muscle strength testing of the upper extremities (at Months 18, 24, 30, and 36/EOS only).

- 12-lead ECG (at Months 18, 24, 30, and 36/EOS only).
- ECHO (at Months 24 and 36/EOS only).
- Clinical laboratory tests.
- Liver panel.
- Chimerism assay (at Month 36/EOS only; for post-HSCT subjects only)
- GAG testing in urine.
- IDUA / GAG testing in blood.
- Circulating AFP level (at Months 18, 24, 30, and 36/EOS only).
- PFTs (at Months 18, 24, 30, and 36/EOS only).
- 6MWT (at Months 18, 24, 30, and 36/EOS only).
- Visual acuity test and corneal clouding exam (at Months 24 and 36/EOS only).
- Neurocognitive abilities tests by WASI-II, WPPSI-IV, or BSID-III, and by VABS-II (at Months 18, 24, 30, and 36/EOS only).
- MRI of liver (at Months 18, 24, 30 and 36/EOS only).
- MRI of brain and cervical spine (at Months 24 and 36/EOS only).
- Immunogenicity assays (at Months 18 and 24 only).

## 6.10 Early Termination

Subjects who discontinue from the study prematurely or are withdrawn from the study will be asked to return to the study site for an Early Termination visit (ETV).

It is at the discretion of the Principal Investigator, in consultation with the Medical Monitor, to waive any procedure if the procedure has been performed within the standard interval of scheduled study visits per protocol.

The following assessments and procedures will be performed:

- Review and record concomitant medications.
- Physical exam.
- Vital signs.
- Assessment of AEs.
- ERT administration log.
- JROM.
- Neurologic cranial nerve exam and muscle strength testing of the upper extremities.
- 12-lead ECG.
- ECHO.
- Clinical laboratory tests.

- Liver panel.
- Chimerism assay.
- GAG testing in urine.
- IDUA / GAG testing in blood.
- Circulating AFP level.
- PFTs.
- 6MWT.
- Visual acuity test and corneal clouding exam.
- Neurocognitive abilities tests by WASI-II, WPPSI-IV, or BSID-III, and by VABS-II.
- MRI of liver.
- MRI of brain and cervical spine.

#### **6.11 ERT Withdrawal (any time after Week 12)**

Subjects who are willing and who are at least 12 weeks post administration of SB-318 may be considered for withdrawal of ERT by the Principal Investigator after consultation with the Sponsor. If undergoing ERT withdrawal, subjects must be medically stable and agree to increased safety monitoring and laboratory testing until the ERT Withdrawal Follow-Up visit.

The ERT Withdrawal visit may occur concurrently or independent of a regular scheduled visit.

The ERT Withdrawal visit should be combined with a regular scheduled visit whenever possible to reduce study burden.

The following assessments and procedures will be performed:

- Review and record concomitant medications.
- Physical examination.
- Vital signs.
- Assessment of AEs.
- ERT administration log.
- Clinical laboratory tests.
- Liver panel.
- GAG testing in urine.
- IDUA / GAG testing in blood.
- PFTs.
- 6MWT.

**6.12 ERT Withdrawal Monitoring (ERT Withdrawal Weeks 1, 2, 3, 4, 6, 8, 10, and 12 [+/- 2 days])**

ERT Withdrawal Monitoring visits will take place on a weekly basis for the first 4 weeks, and on a biweekly basis for the last 8 weeks following the ERT Withdrawal visit until the ERT Withdrawal Follow-Up visit.

ERT Withdrawal Monitoring visits should be combined with regular scheduled visits whenever possible to reduce study burden, and may be conducted remotely.

The following assessments and procedures will be performed:

- Review and record concomitant medications.
- Assessment of AEs.
- ERT administration log.
- Liver panel.
- GAG testing in urine.
- IDUA / GAG testing in blood.

**6.13 ERT Withdrawal Follow-Up (up to 12 weeks post-ERT Withdrawal visit)**

The ERT Withdrawal Follow-Up visit can occur at any time up to 12 weeks after the ERT Withdrawal visit at the discretion of the Principal Investigator.

The following assessments and procedures will be performed:

- Review and record concomitant medications.
- Physical examination.
- Vital signs.
- Assessment of AEs.
- ERT administration log.
- Clinical laboratory tests.
- Liver panel.
- GAG testing in urine.
- IDUA / GAG testing in blood.
- PFTs.
- 6MWT.
- ERT clinical assessment.

## 7 INVESTIGATIONAL PRODUCT AND OTHER STUDY MEDICATIONS

### 7.1 SB-318

SB-318 is a combination of 3 recombinant adeno-associated virus serotype 2/6 (rAAV2/6) vectors that encode:

- ZFN 1 (SB-47171): Left-side ZFN that targets base pairs 447-461 of the albumin locus relative to the transcription initiation site (ZFN 1 product vials are labeled as SB-A6P-ZLEFT).
- ZFN 2 (SB-47898): Right-side ZFN that targets base pairs 468-485 of the albumin locus relative to the transcription initiation site (ZFN 2 product vials are labeled as SB-A6P-ZRIGHT).
- hIDUA Donor (SB-IDUA): DNA repair template that encodes a promotorless human iduronidase (hIDUA) transgene (hIDUA Donor product vials are labeled as SB-A6P-HRL).

Purified lots of recombinant vector are formulated in phosphate buffered saline (PBS) containing CaCl2, MgCl2, NaCl, Sucrose & Kolliphor (Poloxamer) P 188 and filled at volumes of either 5 mL or 10 mL into vials, which are then stored at ≤-65°C. The lots are tested for identity, sterility, potency, and stability.

#### 7.1.1 Inventory, Storage, and Handling of the Drug Product

The SB-318 components required for subject treatment will be shipped to the study center with dry ice and temperature monitoring device, and must be stored at ≤ -65°C (with temperature monitoring) prior to administration.

A Clinical Certificate of Analysis for each SB-318 component will accompany each shipment. The vials will have a label affixed containing the following information: vector identity, lot number, concentration, volume, storage conditions, manufacturer, date of manufacturing, sponsor, and "Caution: For investigational use only".

Shipments will consist of subject-specific kits that comprise the 3 SB-318 components in the quantities required based on the subject's weight and cohort. Kit labels will contain the following additional information: subject ID number, protocol number, and quantity.

The study center is required to maintain complete records of all study products received during the course of this study, as well as of labeled product that is dispensed. At the conclusion or termination of this study, return or destruction of all drug supplies must be coordinated with Sangamo (refer to the Pharmacy Manual for additional details).

The Principal Investigator agrees not to supply labeled product to any person other than study personnel and subjects in this study.

#### 7.1.2 SB-318 Administration

SB-318 will be shipped to the study site prior to the scheduled infusion. On Day 0, after the subject has arrived at the hospital or acute care facility and has been confirmed to be eligible for infusion, the 3 components of SB-318 (ZFN1, ZFN2, and hIDUA Donor) will be thawed by placing the vials at room temperature. Then each component will be added to 200 mL of diluent (refer to the

Pharmacy Manual) and adjusted to 0.25% human serum albumin. Total infusion volumes will be calculated according to the subject's cohort assignment and body weight (kg).

Once the SB-318 infusion is prepared it should be transported at room temperature to the infusion facility at the hospital or acute care facility, and be kept at room temperature prior to infusion. SB-318 will be infused while monitoring the subject's vital signs (temperature, heart rate, respiratory rate, and blood pressure) pre-, during, and post-infusion (for frequency, refer to the Study Reference Manual) until discharge.

For detailed instructions for thawing and infusing SB-318, refer to the Pharmacy Manual.

Side effects following SB-318 infusions may include transient fever, chills, and/or nausea. These symptoms can be treated with acetaminophen (Tylenol or Paracetamol) 650 mg by mouth and diphenhydramine hydrochloride (Benadryl) 25-50 mg by mouth or IV or equivalent medication. These medications may be repeated every 3-4 hours as needed.

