**Exclusion Criteria**

	

1. Known to be unresponsive to ERT.

2. Neutralizing antibodies in serum (immune response) to AAV2/6.

3. Serious intercurrent illness or clinically significant organic disease (unless secondary to MPS I) such as cardiovascular, hepatic, pulmonary, neurologic, or renal disease.

4. Receiving antiviral therapy for hepatitis B or C, or with active hepatitis B (HBV DNA positive or HBV surface antigen positive) or hepatitis C (HCV RNA viral load) or human immunodeficiency virus (HIV)-1/2 (HIV RNA viral load or HIV antibody positive); to be considered negative for hepatitis C after treatment of an active HCV infection, viral assays in 2 samples collected at least 6 months apart must be negative.

5. Lack of tolerance to ERT with significant infusion-associated reactions (IARs) or occurrence of anaphylaxis.

6. Polymorphisms in the ZFN-targeted region of the albumin locus.

7. Liver fibrosis score of 3 or 4 on a 0 to 4 point scale (Desmet et al. 1994) if subject has had a liver biopsy within 2 years of Screening.

8. Markers of hepatic dysfunction as evidenced by one or more of the following:

a. Platelet count <100,000/<math>\mu</math>L.

b. Albumin <math>\leq</math>3.2 g/dL.

c. Total bilirubin <math>></math>1.5 x upper limit of normal (ULN) and direct bilirubin <math>\geq</math>0.5 mg/dL.

d. Alkaline phosphatase <math>></math>2.0 x ULN.

e. Alanine aminotransferase (ALT) or aspartate aminotransferase (AST) <math>></math>2.0 x ULN.

9. Creatinine <math>\geq</math> 1.5 mg/dL.

10. Weight <math><</math> 20 kg at Screening.

11. Pregnant or breastfeeding female.

12. Contraindication to the use of corticosteroids.

--	---

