## **4 SUBJECT SELECTION**

### **4.1 Inclusion Criteria**

Subjects must meet all of the following criteria to be included in the study:

1. Signed informed consent.
2.  $\geq 5$  years of age:
  - a) adult cohorts 1 through 3:  $\geq 18$  years of age;
  - b) pediatric cohorts 4 and 5: 12 to 17 years of age; and
  - c) pediatric cohorts 6 and 7: 5 to 11 years of age.
3. Clinical diagnosis of MPS I; IDUA deficiency confirmed by gene sequencing.
4. Sexually mature subjects must agree to use a barrier contraceptive method for prevention of AAV transfer as follows: for female subjects this means that the subjects' partners must use a condom from dosing with SB-318 until at least 3 consecutive plasma samples after administration of SB-318 are negative for AAV2/6; for male subjects this means that the subjects must use a condom and must refrain from sperm donation from the time of SB-318 until at least 3 consecutive semen samples after administration of SB-318 are negative for AAV2/6. Additionally, female participants of child-bearing potential must consent to use a highly effective method of contraception.
5. Magnetic resonance imaging (MRI) negative for liver mass as read by a radiologist.

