## **6 STUDY METHODOLOGY**

Prior to initiation of this study, the study site shall be approved by the IRB/IEC or equivalent. Subjects must be willing to participate in all study procedures related to this protocol.

The following sections describe all study procedures. Additional detailed instructions will be provided in the Study Reference Manual, Laboratory Manual, and Pharmacy Manual. A table of all study procedures is presented in the Schedule of Events (see [Appendix 1](#)).

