### 11.3 Pediatric Dosing

Pediatric dosing will not be initiated until adult safety data has been obtained and reviewed by the SMC, and only after the following conditions have been met:

- $\geq$ 6 months of safety data from 2 adults treated with SB-318 at any dose; and
- $\geq$ 4 weeks of safety data from 2 adults treated with SB-318 at the intended pediatric dose.

Younger pediatric subjects (Cohorts 6 and 7) may not be dosed until older pediatric subjects (Cohorts 4 and 5) have been dosed at the same dose level, and  $\geq 4$  weeks of safety data from each older subject has been reviewed by the SMC.

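### Section 7.1.2 offers fixed amounts of acetaminophen and diphenhydramine with no age or weight limit, although children from 5 years and 20 kg may enrol

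*Protocol*

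**What the plan says.** Protocol Section 7.1.2 describes how infusion symptoms may be handled. They can be "treated with acetaminophen (Tylenol or Paracetamol) 650 mg by mouth and diphenhydramine hydrochloride (Benadryl) 25-50 mg by mouth or IV or equivalent medication". The next sentence reads: "These medications may be repeated every 3-4 hours as needed". Neither sentence mentions cohort, age, weight or a daily maximum.

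Section 7.1.2 applies to every subject who receives SB-318. Section 4.1 opens entry to "pediatric cohorts 6 and 7: 5 to 11 years of age", and exclusion criterion 10 removes only those weighing less than "20 kg at Screening".

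The other mentions of the two drugs give no amount. Protocol Section 7.2, SAP Section 8.1.7 and the notes to SAP shell Table 14.1.5 deal only with recording them as concomitant medication.

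On the surrounding safeguards, Section 6.4 has subjects treated in a hospital or acute care facility and says they will "remain there for at least 24 hours after the infusion for observation". Section 11.3 states: "Pediatric dosing will not be initiated until adult safety data has been obtained and reviewed by the SMC".

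**The concern.** The protocol gives one amount of each drug for a population that runs from a 20 kg child to an adult. A clinician who follows the only figure on the page gives a small child the adult amount.

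The protocol takes body size into account elsewhere. SB-318 is dosed per kg (Section 3.3). Prednisone is banded by weight and switches to mg/kg below 30 kg (Appendix 3). Pediatric blood draws are limited to 0.8 mL/kg in any 24 hours (Section 9.33). Section 7.1.2 makes no such adjustment.

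What is at stake is dosing safety for supportive care in Cohorts 4 to 7, most of all in Cohorts 6 and 7. No endpoint, analysis set or estimate depends on it.

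**Working it through.** The plan states no derived figure to reproduce. The check is direct arithmetic.

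**Inputs**
- Acetaminophen 650 mg, diphenhydramine 25-50 mg, interval 3-4 hours: Protocol Section 7.1.2.
- Lowest eligible weight 20 kg: exclusion criterion 10. This is the entry floor, not a typical weight.
- 30 kg: an illustrative heavier child.
- Adult weight 40 to 80 kg: an assumption, since the documents give no adult weights.
- Cohort sizes: Protocol Section 3.5.

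**Acetaminophen per dose** (amount / weight)

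| Weight | mg/kg per dose |
|---|---|
| 20 kg | 650/20 = 32.5 |
| 30 kg | 650/30 = 21.7 |
| 40 kg (assumed adult, low) | 650/40 = 16.25 |
| 80 kg (assumed adult, high) | 650/80 = 8.125 |

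Ratio at 20 kg: 32.5/16.25 = 2.0 and 32.5/8.125 = 4.0. Ratio at 30 kg: 40/30 = 1.3 and 80/30 = 2.7. The amount that would match the adult per-kg amount at 20 kg is 8.125 × 20 = 162.5 mg to 16.25 × 20 = 325 mg.

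**Diphenhydramine per dose**
- At 20 kg: 25/20 = 1.25 to 50/20 = 2.5 mg/kg.
- At 40 kg: 25/40 = 0.625 to 50/40 = 1.25 mg/kg.
- At 80 kg: 25/80 = 0.31 to 50/80 = 0.625 mg/kg.

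So the lower stated amount at 20 kg equals, per kg, the upper stated amount at 40 kg.

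**What the interval alone permits:** 24/4 = 6 to 24/3 = 8 doses in 24 hours. For acetaminophen that is 6 × 650 = 3,900 mg to 8 × 650 = 5,200 mg. This is a ceiling under continuous repetition, not expected use. Its only role here is to show why the pediatric source named in the fix should carry a daily maximum.

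**How many subjects it could touch:** the initial plan is 1 + 6 × 2 = 13 subjects, of whom 4 × 2 = 8 are in Cohorts 4 to 7 (4 aged 12-17 and 4 aged 5-11). Some of these cohorts are conditional, and some adolescents may weigh as much as the assumed adults.

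**The case against.** The strongest reply is that Section 7.1.2 offers an option and is not a dosing rule. It says symptoms can be treated this way, allows an equivalent medication, and leaves repeats to need. Treatment is given under hospital observation for at least 24 hours, so a clinician chooses the drug and the amount. This stands. A reader might infer that every child would receive 650 mg; the text supports only that it allows it.

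Second, the multiple of 2 to 4 is simply a ratio of body weights (40/20 and 80/20) and would arise with any fixed amount. That also stands. It describes exposure per kg and is not evidence of harm.

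Third, the manuals may deal with children. Section 6 says: "Additional detailed instructions will be provided in the Study Reference Manual, Laboratory Manual, and Pharmacy Manual". They were not available for this review, so it cannot be said that pediatric amounts are missing from the trial's instructions, only that the protocol does not state them. Section 7.1.2 itself does not send the reader to a manual for these two drugs. Its closing pointer is "For detailed instructions for thawing and infusing SB-318, refer to the Pharmacy Manual".

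Fourth, pediatric exposure is conditional. Doses for Cohorts 4 to 7 are still to be set, Section 11.3 requires adult data and SMC review first, and the SAP table shells show only the 1.00E+13 and 5.00E+13 vg/kg columns. This lowers the urgency. It does not settle whether children will be dosed, because the 5.00E+13 column could include a child and both documents still plan those cohorts.

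Finally, nothing in the documents shows a problem with adult use, so a 24-hour maximum for adults is a preference and not a correction.

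**Conclusion.** The point holds as a minor patient-safety correction. The protocol states fixed amounts with no age or weight limit while admitting children from 5 years and 20 kg. Used unchanged, the acetaminophen amount would be 32.5 mg/kg per dose at 20 kg, 2 to 4 times the per-kg amount at an assumed adult weight of 40 to 80 kg. At 30 kg the multiple falls to 1.3 to 2.7.

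A reader might go further and conclude that the stated amounts are toxic to a small child, or that the 6 to 8 doses a day permitted by the interval represent expected exposure. The documents support neither. They give no dose threshold for either drug, and repeats are only as needed.

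The size rests on the 20 kg entry floor, the assumed adult weights, and the amounts being used as written. There is no effect on sample size, endpoints, data collection or analysis.

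**What to change.** Before any dosing in Cohorts 4 to 7, add one qualification to Section 7.1.2, along these lines: *The amounts above apply to adult Cohorts 1 to 3 only. In Cohorts 4 to 7, dose both drugs by weight under local pediatric labeling or [named manual], within that source's 24-hour maximum.* The pediatric amounts themselves must come from that source, since the documents contain none. If a manual already covers this, naming it in Section 7.1.2 is enough. A 24-hour maximum for adults is optional.

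This is a cheap improvement. The cost is a short amendment needing written IRB/IEC approval (Section 14.3) and biosafety committee submission as appropriate (Section 14.2), at approximately 12 to 15 sites. It can go with the next amendment, provided that amendment takes effect before the first child is dosed.
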